##### Early treatment failure (ETF)

Patients will be classified as ETF upon meeting any of the following criteria:

- Clinical decline or lack of improvement (per Investigator) at 24 hours after first dose of treatment.

- Development of any clinical complications (described in the WHO definition of complicated/severe malaria (WHO Guidelines 2010) in the presence of parasitaemia (based on microscopy) within 72 hours of the first dose of treatment
- Parasitaemia  $> 75\,000/\mu\text{L}$  based on microscopy at or after 12 hours post first dose
- Parasitaemia  $\geq$  baseline based on microscopy with or without fever at 36 hours after the first dose of treatment
- Any parasitaemia based on microscopy with fever, 48 hours post first dose
- Parasitaemia  $> 100/\mu\text{L}$  based on microscopy with or without fever, 72 hours post first dose

### **Late Clinical Failure (LCF)**

Patients will be classified as LCF upon meeting any of the following criteria:

- Development of danger signs or severe malaria on any day between Study Day 5 and Study Day 29 in the presence of parasitaemia based on microscopy without previously meeting any of the criteria of ETF.
- Presence of parasitaemia based on microscopy and fever (i.e. axillary temperature  $\geq 37.5^\circ\text{C}$  or other routes  $\geq 38^\circ\text{C}$ ) on any day between Study Day 5 and Study Day 29 without previously meeting any of the criteria of ETF.

### **Late Parasitological Failure (LPF)**

Patients will be classified as LPF upon meeting the following criterion:

- Presence of parasitaemia based on microscopy on any day between Study Day 5 and Study Day 29 and no fever (i.e. axillary temperature  $< 37.5^\circ\text{C}$  or other routes  $< 38^\circ\text{C}$ ) without previously meeting any of the criteria of ETF or LCF.

### **Adequate Clinical and Parasitological Response (ACPR):**

Absence of parasitaemia based on microscopy on Study Day 29 irrespective of axillary temperature, without previously meeting any of the criteria of ETF, LCF, or LPF.

### **Uncorrected ACPR at Day X where X=15 and 29**

- A patient is considered as non-responder at Day X if the patient experiences an ETF, LCF or LPF from Day 5 to Day X.
- A patient is also considered as non-responder if the parasitaemia is not cleared by Day X unless the patient discontinues the study prior to Day X without ETF, LCF, or LPF in which case the response is considered as missing.

- A patient is considered as responder (Uncorrected ACPR) at Day X if the patient is not classified as a non-responder at Day X and the patient has a malaria blood film showing absence of parasitaemia at Day X or later if Day X is missing.
- The response for a patient is considered as missing/undertermined if the patient is not classified as a non-responder and the malaria blood film result at Day X is missing and not followed by a subsequent negative result.

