#### 2.1.1 General definitions

**Study treatment:** KAE609 is the investigation treatment whereas Coartem® will serve as control. They are referred to as study treatments in the document.

Summary results will be presented by cohort and treatment group. Besides, a pooled Coartem group from all cohorts will be presented from all tables as applicable. The following abbreviated treatment group labels will be used as the column headers in the CSR outputs:

- KAE609 10 mg SD

- KAE609 10 mg QD 3 days
- KAE609 25 mg SD
- KAE609 25 mg QD 3 days
- KAE609 50 mg SD
- KAE609 50 mg QD 3 days
- KAE609 75 mg SD
- KAE609 150 mg SD
- KAE609 225 mg SD or KAE609 110 mg SD
- Coartem
- Pooled Coartem

**Baseline:** The last measurement made prior to and including administration of the first dose of study treatment. Note this may include measurements taken on the day of randomization (e.g. lab, ECG, vital signs). If a patient did not receive any dose of study treatment then the randomization date will be used as the date of first dose of study treatment.

**Study day:** Study day will be calculated with respect to the first dose of study treatment. The first day of administration of study treatment (first dose) is defined as Day 1. Day -1 will be the day before Day 1. Day 0 does not exist. If a patient did not receive any dose of study treatment then the randomization date will be used as the date of first dose of study treatment.

For assessments collected on or after Day 1, study day = date of assessment – date of first dose of study treatment + 1.

For assessments collected prior to Day 1, study day = date of assessment - date of first dose of study treatment.

At the end of trial, full statistical analyses will be performed by cohort and treatment group. Coartem data from all cohorts will also be pooled.

Tail of KM plots: Since the tail of KM plots after the day of last planned assessment is not reliable due to small numbers of patients at risk, the time to event will be truncated to the planned last day (Day 29) regardless of censoring.

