### **PCR-corrected ACPR at Day X where X=15 and 29**

- A patient is considered as non-responder at Day X if the patient experiences an ETF, LCF, or LPF from Day 5 to Day 7.
- A patient is also considered as non-responder if the parasitaemia is not cleared by Day X unless the patient discontinues the study prior to Day X without ETF, LCF, or LPF, in which case the response is considered as missing,
- A patient is considered as non-responder at Day X if the patient has a parasite recrudescence from Day 8 to Day X
- A patient is considered as responder (corrected ACPR) at Day X if the patient is not classified as a non-responder by Day 7 and has a new infection from Day 8 to Day X based on PCR genotyping unless that the patient did not have parasites cleared prior to the new infection, in which case the patient is considered as non-responder.
- A patient is considered as responder at Day X if the patient is not classified as a non-responder at Day X and the patient has a malaria blood film showing absence of parasitaemia at Day X or later if Day X is missing.
- The response for a patient is considered as missing/undetermined if
  - The patient has parasitaemia present from Day 8 to Day X for which the PCR genotyping of recrudescence or new infection is not determined.
  - The patient is not classified as a non-responder at Day X and the malaria blood film result at Day X is missing and not followed by a subsequent negative result.

Note - The outcome of PCR-corrected ACPR and uncorrected ACPR at a given day is categorized as responder or non-responder to distinguish from failure used in early treatment failure, late clinical failure or late parasitological failure. With this notation, ACPR rate is the proportion of responders.

A patient with presence of parasitaemia at more than 7 days after the first dose is considered as non-responder for uncorrected ACPR. We reclassify such a patient as responder for PCR-corrected ACPR if presence of parasitaemia at more than 7 days after the first dose is due to new infection. Whether the presence of parasitaemia after 7 days is due to recrudescence or new infection is determined and provided by the central laboratory.

The above definitions of ACPRs are purely based on the malaria blood film and PCR results without consideration for taking concomitant anti-malaria drugs. In statistical analyses, some

responses may be overridden for patients who take concomitant anti-malaria drugs (see [Sections 2.5 and 2.7](#)).

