#### 2.7.2.1.1 Analysis of PCR-corrected ACPR using Kaplan-Meier method

For the FAS, the proportion of patients with PCR-corrected ACPR at Day 29 and 95% CI will be also estimated using the Kaplan-Meier method ([Stepniewska and White 2006](#) and [WHO 2015](#))

**Event** = PCR-corrected non-responder during the study (same as at Day 29, See Section 2.1). The event time is the first time when the patient becomes a non-responder based on PCR-correction. If a patient parasite is not cleared at all, Day 7 is considered as the event time.

The PCR-corrected responder rate at Day 29 is estimated by the survivor function at Day 29 using the Kaplan-Meier method.

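### The SAP's ACPR rules count early treatment failure only from Day 5 if read literally, although five of the six ETF criteria can be met only on Study Days 1 to 4

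*SAP*

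**What the plan says.** SAP 2.1.1.1 gives a general definition of ACPR and then operational rules for Day 15 and Day 29.

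- **General definition (Study Day 29 only):** no parasitaemia on that day, "without previously meeting any of the criteria of ETF, LCF, or LPF". No start day is attached to ETF. Protocol 6.5.8 agrees.
- **Uncorrected ACPR at Day X:** "A patient is considered as non-responder at Day X if the patient experiences an ETF, LCF or LPF from Day 5 to Day X".
- **PCR-corrected ACPR at Day X:** non-responder "if the patient experiences an ETF, LCF, or LPF from Day 5 to Day 7", with recrudescence counted from Day 8.
- **Responder, both versions:** not classified as a non-responder, with a negative film at Day X, or later if Day X is missing.
- **Antimalarial use:** the note after the PCR-corrected rule says the definitions disregard concomitant antimalarials and that responses may be overridden under Sections 2.5 and 2.7. The handling list in SAP 2.7.2.1 deals only with antimalarials that are not rescue.
- **Kaplan-Meier (SAP 2.7.2.1.1 and 2.7.2.1.2):** the event is the same Day 29 non-responder status.

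Protocol 9.5.1.1 counts rescue for *P. falciparum* malaria as treatment failure, except when it treats a new infection. SAP Section 4 declares no change from the protocol analyses.

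**The concern.** The Day 5 start fits late clinical failure (LCF) and late parasitological failure (LPF), which begin on Study Day 5 by definition. It does not fit ETF, which is nearly always over by then. If the date range governs the whole list, most early failures fall outside the window in which failures are counted.

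ETF leads to rescue (protocol 5.5.6), and rescued patients stay in follow-up, so their Day 15 and Day 29 films are still taken. A negative film would then reflect the rescue drug but be credited to the randomised treatment. Any inflation of ACPR would fall mainly where early failures occur. The protocol itself expects sub-therapeutic efficacy in Cohorts 1 and 2, so the efficacy dose-response could look flatter than it is.

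**Working it through.** The documents state no expected ACPR rate, so there is no planned figure to reproduce. The check maps times to days, traces the rules, and sizes the effect per patient.

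**Step 1. When can each ETF criterion be met?** SAP 2.1.1: "The first day of administration of study treatment (first dose) is defined as Day 1". With the first dose at clock hour c (0 ≤ c < 24), a nominal time h hours later falls on Study Day floor((c + h)/24) + 1.

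| ETF criterion (SAP order) | Nominal time | Possible Study Days |
|---|---|---|
| 1. "Clinical decline or lack of improvement (per Investigator) at 24 hours after first dose of treatment" | 24 h | 2 |
| 2. Clinical complications with parasitaemia, "within 72 hours of the first dose of treatment" | 0 to 72 h | 1 to 4 |
| 3. Above 75 000/µL "based on microscopy at or after 12 hours post first dose" | 12 h onward, no end | 1 onward |
| 4. At or above baseline count | 36 h | 2 or 3 |
| 5. Any parasitaemia with fever | 48 h | 3 |
| 6. Above 100/µL | 72 h | 4 |

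Only criterion 3 can fall on Day 5 or later. SAP Table 5-6 agrees on the 72-hour count: its analysis window closes on Day 4.

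**Step 2. Trace a patient with ETF on Days 1 to 4 who clears on rescue.**

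- First non-responder bullet, literal reading: not met, because the ETF precedes Day 5.
- Later LCF or LPF: excluded, because both require no previous ETF.
- Parasitaemia not cleared by Day X: not met after clearance.
- Rescue rule: none in SAP 2.7.2.1, and no rescue override of the response in Section 2.5 or 2.7.
- Responder bullet: met.
- Kaplan-Meier: not an event, so censored at the last parasitaemia assessment.

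| Day of ETF (films negative at Days 15 and 29) | Literal Day 5 start | ETF counted on any day |
|---|---|---|
| 1, 2, 3 or 4 | responder | non-responder |
| 5 | non-responder | non-responder |

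The result is the same for X = 15 and X = 29.

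**Step 3. Size.** One reclassified patient moves the rate by 1/n: 1/10 = 10 points and 1/20 = 5 points. KAE609 arms are planned at 10 in Cohorts 1 and 2 and at 20 in later cohorts.

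For illustration, suppose all other patients respond and all ETF patients clear on rescue. Exact 95% limits are BetaInv(0.025; x, n − x + 1) and BetaInv(0.975; x + 1, n − x). When x = n they become 0.025^(1/n) and 1.

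| n | ETF patients | Literal rule | ETF counted |
|---|---|---|---|
| 10 | 1 | 10/10 = 100% (69.2 to 100) | 9/10 = 90% (55.5 to 99.7) |
| 10 | 4 | 10/10 = 100% (69.2 to 100) | 6/10 = 60% (26.2 to 87.8) |
| 20 | 1 | 20/20 = 100% (83.2 to 100) | 19/20 = 95% (75.1 to 99.9) |
| 20 | 5 | 20/20 = 100% (83.2 to 100) | 15/20 = 75% (50.9 to 91.3) |

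**The case against.** **The sentence has another reading.** The date range can attach to LCF and LPF alone, which matches their own windows. On the literal reading, listing ETF does almost nothing. The second bullet of each rule names ETF with no start day, and the general definition just above excludes any earlier ETF. Protocol 6.5.8 and 9.5.1.1 point the same way. This stands: a reader might infer that rescued ETF patients will be reported as responders, and the documents do not establish that. They show two conflicting instructions.

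It does not remove the point. The modifier follows the whole list, and the Day X rules are the detailed derivation that would be programmed. The general definition covers Study Day 29 only, so for Day 15 the Day X rule is the only definition in the SAP. The protocol's rescue rule would have been a backstop, but the SAP does not carry it over.

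**The consequence is limited.** Efficacy is secondary and descriptive, with no comparison against Coartem. The proportion with ETF is tabulated separately with exact intervals, so early failures remain visible. This also stands. Even so, under the literal rule an arm could show a substantial ETF proportion beside near-complete ACPR.

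**Earlier ETF rates do not give an estimate.** Protocol 3.6 reports three ETF patients at 10 mg (42%) and one at 20 mg (25%), but none at 15 mg or 30 mg. A reader might infer an overstatement of about 40 points at 10 mg and 25 points near 20 to 25 mg. The documents do not support that. The groups were very small, denominators are not given, the 20 mg figure is one patient, and nothing shows that the same ETF criteria were used.

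**Conclusion.** The operational ACPR rules are wrong as written. Taken literally, they classify a patient with ETF on Days 1 to 4 who clears on rescue as a responder at Day 15 and Day 29, for both uncorrected and PCR-corrected ACPR, and as censored in both Kaplan-Meier analyses. This conflicts with the general ACPR definition in both documents and with the protocol's rescue rule, while SAP Section 4 declares no change.

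The supported size is per patient: 10 points in an arm of 10 and 5 points in an arm of 20. It assumes that the patient clears on rescue, has a negative film at Day X, and is analysed in an arm of the planned size. How many patients would be affected cannot be derived from the documents. The primary hepatic endpoint and the sample size do not depend on this rule.

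**What to change.** 1. In the uncorrected rule, replace the first bullet by wording such as: *non-responder at Day X on meeting any ETF criterion at any time after the first dose, or on LCF or LPF between Day 5 and Day X*.
2. In the PCR-corrected rule, make the same change with the late-failure window ending at Day 7.
3. Add to SAP 2.7.2.1 the protocol 9.5.1.1 rule that rescue for *P. falciparum* malaria is failure, with its exception for a new infection. This supplies the override to which the SAP note refers.

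No separate Kaplan-Meier rule is needed. The SAP already sets the event time at the first time a patient becomes a non-responder.

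Separately, the passages that end ETF complications at 72 hours and start LCF and LPF on Study Day 5 should be reconciled. Those criteria also govern rescue, so this review does not propose the rule.

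The cost is a few SAP sentences and the matching derivation, with no new data. If the literal rule has been programmed, ACPR may fall in arms with early failures.

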### **PCR-corrected ACPR at Day X where X=15 and 29**

- A patient is considered as non-responder at Day X if the patient experiences an ETF, LCF, or LPF from Day 5 to Day 7.
- A patient is also considered as non-responder if the parasitaemia is not cleared by Day X unless the patient discontinues the study prior to Day X without ETF, LCF, or LPF, in which case the response is considered as missing,
- A patient is considered as non-responder at Day X if the patient has a parasite recrudescence from Day 8 to Day X
- A patient is considered as responder (corrected ACPR) at Day X if the patient is not classified as a non-responder by Day 7 and has a new infection from Day 8 to Day X based on PCR genotyping unless that the patient did not have parasites cleared prior to the new infection, in which case the patient is considered as non-responder.
- A patient is considered as responder at Day X if the patient is not classified as a non-responder at Day X and the patient has a malaria blood film showing absence of parasitaemia at Day X or later if Day X is missing.
- The response for a patient is considered as missing/undetermined if
  - The patient has parasitaemia present from Day 8 to Day X for which the PCR genotyping of recrudescence or new infection is not determined.
  - The patient is not classified as a non-responder at Day X and the malaria blood film result at Day X is missing and not followed by a subsequent negative result.

Note - The outcome of PCR-corrected ACPR and uncorrected ACPR at a given day is categorized as responder or non-responder to distinguish from failure used in early treatment failure, late clinical failure or late parasitological failure. With this notation, ACPR rate is the proportion of responders.

A patient with presence of parasitaemia at more than 7 days after the first dose is considered as non-responder for uncorrected ACPR. We reclassify such a patient as responder for PCR-corrected ACPR if presence of parasitaemia at more than 7 days after the first dose is due to new infection. Whether the presence of parasitaemia after 7 days is due to recrudescence or new infection is determined and provided by the central laboratory.

The above definitions of ACPRs are purely based on the malaria blood film and PCR results without consideration for taking concomitant anti-malaria drugs. In statistical analyses, some

responses may be overridden for patients who take concomitant anti-malaria drugs (see [Sections 2.5 and 2.7](#)).

**Fever Clearance time (FCT)**, defined as time from the first dose until the first time the axillary body temperature decreased below and remained below 37.5°C axillary or 38.0°C oral/tympanic/rectal for at least a further 24 hours.

**Parasite clearance time (PCT)**, defined as time from the first dose until the first total and continued disappearance of asexual parasite forms which remained at least a further 48 hours.

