5.5.4 Instructions for prescribing and taking study treatment

KAE609

KAE609 can be administered irrespective of the timing of food intake.

Study medication will be administered by the study center personnel with approximately 180-240 ml of water. Each subject's mouth must be checked to ensure that the medication was swallowed. In the case that the patient vomits within 30 minutes of intake a replacement dose will be given to the patient and the investigator or designee will notify IRT. If the second dose is vomited the patient has to be given Coartem as rescue medication.

Coartem

Patients will be dosed BID for 3 days (at the following time points: 0, 8, 24, 36, 48, and 60 hours) and must receive a standard meal within 30 min prior to dosing, as per label. In the case that the patient vomits within 1 hour of intake a replacement dose will be given to the patient and the investigator or designee will notify IRT. If the second dose is vomited the patient has to be given non-lumefantrine standard of care.

Conventional 80/480 mg tablets or 20/120 mg tablets are to be taken orally with a glass of water. The dispersible tablet is to be dissolved in 10 mL of water in a small cup, and subsequently administered orally under hospital supervision; thereafter the cup will be rinsed with an additional 10 mL of water and the content is to be swallowed again.

Coartem medication should be followed whenever possible by food/drink (broth, sweetened condensed milk, etc.) as appropriate.

All dosages prescribed and dispensed to the subject during the study must be recorded on the Dosage Administration Record (DAR) CRF.

All kits of study treatment assigned by the IRT will be recorded in the IRT.

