9.5.1.1 PCR-corrected ACPR and uncorrected ACPR

At each visit, the ACPR rate with 95% confidence intervals will be provided using the Pearson-Clopper method for each treatment group by cohort.

Data will be handled as follows:

- Treatment failures after 7 days (i.e., Study Day 8) due to reinfection based on PCR genotyping are not considered as failure for PCR-corrected analyses.
- For parasitological uncorrected ACPR, patients will be treated as failure on and after the visit when a new infection (i.e., reinfection) with *P. falciparum* or other species is detected.
- Patients who received rescue medication for the treatment of *P. falciparum* malaria (except for the treatment of a new infection) will be considered treatment failures. Patients who received other concomitant medication having an effect on malaria for reasons other than rescue therapy e.g., for the treatment of *P. vivax* (e.g., primaquine, certain antibiotics (sulfonamides, tetracycline, etc.)) will be considered in the analysis as if they had not taken the drug.
- Patients will be counted as failure at a visit (e.g., Study Day 15, etc.) if (a) they did not have a parasite count i.e., missing parasite count at that visit unless these patients could be classified as cured based on absence of parasitaemia (parasite count = 0) at a later time (e.g., Study Day 29), or (b) they did not have valid PCR evaluations at baseline and the visit if parasitaemia was present at that time (e.g., Study Day 15).

In addition, PCR-corrected ACPR rate will be calculated and plotted using the Kaplan-Meier method ([Stepniewska and White 2006](#); [WHO 2016](#)) for each treatment group by cohort in the FAS. Treatment failure is the event for analysis and patients without Study Day 29 data and treatment failure is considered as censored instead of treatment failure. The PCR-corrected ACPR rate at Study Day 29 is estimated by the survival function at Study Day 29. Patients who had a new infection (i.e., reinfection) with *P. falciparum* or other species without *P. falciparum* recrudescence on or after Study Day 8 will be censored at the time of the first PCR that indicate the infection; patients who took antimalarial medications for reinfection or reasons other than

rescue medication given for *P. falciparum* related treatment failure will be censored at the first time of such antimalarial medications; other patients without treatment failure will be censored at the time of last parasitaemia assessment.

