## 2 Statistical methods

### 2.1 Data analysis general information

Data will be analyzed by [REDACTED] on behalf of Novartis for the interim safety assessment and after final DBL using SAS version 9.4 according to the data analysis presented in section 9 of the study protocol which will also be available in [Appendix 16.1.1 of the CSR](#). Important information is given in the following sections and details will be provided, as applicable, in [Appendix 16.1.9 of the CSR](#).

At the end of trial, full statistical analyses will be performed by cohort and treatment group. Coartem data from all cohorts will also be pooled.

Any data analysis carried out independently by the investigator should be submitted to Novartis before publication or presentation.

Data analyses required for the study SRC meeting will be analyzed by the third party vendor ([REDACTED]). The outline of the SRC Review analysis plan is presented in the SRC charter and will be detailed in the SRC TFL shells. A separate SAP for SRC is not needed since the statistical methods for SRC are same as those in this SAP.

Information on visit windows, imputation rules and the methods of efficacy and safety analyses is given in the sections to follow and details will be provided, as applicable, in [Appendix 16.1.9 of the CSR](#). This SAP covers the methods for both planned interim safety review and the final analysis.

Unless otherwise stated, summary tables/figures/listings will be on all patients included in the population under consideration.

Categorical data will be presented as frequencies and percentages. For continuous data, n, mean, standard deviation, median, 25th and 75th percentiles, minimum, and maximum will be presented. Additionally, geometric mean will be presented for PK parameters which may be better described using the lognormal distribution.

Unless otherwise stated, p-values will be provided for two-sided alternative hypotheses and presented with up to 4 significant digits after decimal place; confidence intervals will be presented with up to 2 significant digits after decimal place.

Since the randomization is not stratified, statistical analysis will not be stratified. For pooled analyses, coartem patients will be pooled from all the cohorts and compared with patients from different KAE doses.

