### **Handling of missing values/censoring/discontinuations**

Data will be handled as follows:

- Patients with presence of parasitaemia which was determined to be reinfection on Day 8 or later will be counted as responders for PCR corrected ACPR and as non-responder for PCR uncorrected ACPR from the day of test
- Patients with presence of parasitaemia which cannot be determined to be recrudescence or reinfection due to missing PCR corrected/uncorrected data will be counted as non-responders from the day of test
- Patients with missing/undetermined responses at a visit due to missing blood smear data at the visit will be counted as non-responders (PCR corrected or uncorrected) unless there is a later blood smear test indicating no parasitemia
- Patients who received non rescue anti-malarial medication will be considered in the analysis as if they had not taken the anti-malarial drug.

In addition, PCR-corrected and uncorrected ACPR rate will be calculated and plotted using the Kaplan-Meier method for each treatment group by cohort in the FAS.

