## 4 Change to protocol specified analyses

NA.

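### SAP 2.7.2.1 omits the protocol rule that rescue for P. falciparum is treatment failure, so as written it can score a rescued patient as an ACPR responder in the full analysis set

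*SAP*

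**What the plan says.** **Protocol 9.5.1.1, proportions.** One bullet holds two rules. Patients who received rescue for P. falciparum malaria ("except for the treatment of a new infection) will be considered treatment failures". Patients who took other drugs with antimalarial effect for other reasons are analysed as though they had not.

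**Protocol 9.5.1.1, Kaplan-Meier.** "Treatment failure is the event for analysis". Patients who took antimalarials for reinfection, or for reasons other than rescue for P. falciparum treatment failure, "will be censored at the first time of such antimalarial medications".

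**SAP 2.1.1.1.** ACPR on Day 15 or 29 is derived from film and PCR without regard to antimalarials taken. The closing note says some "responses may be overridden for patients who take concomitant anti-malaria drugs" and refers to Sections 2.5 and 2.7.

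**SAP 2.7.2.1.** There are four handling rules: reinfection, undetermined PCR, missing smear and non-rescue drugs. The last reads "Patients who received non rescue anti-malarial medication will be considered in the analysis as if they had not taken the anti-malarial drug". Rescue is not mentioned.

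**SAP 2.1 and 4.** Analysis is to run "according to the data analysis presented in section 9 of the study protocol". The section headed "Change to protocol specified analyses" reads NA.

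**Rescue.** Protocol 5.5.4 says of KAE609: "If the second dose is vomited the patient has to be given Coartem as rescue medication". SAP 2.4.2 calls Coartem rescue when it follows early treatment failure (ETF), late clinical failure (LCF) or late parasitological failure (LPF).

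**The concern.** The SAP kept the second half of the protocol's bullet and dropped the first. Its note on overrides sends the programmer to sections that do not supply the missing rule: Section 2.5 is the hepatic endpoint, and Section 2.7 has a rescue rule only for parasite and fever clearance times (2.7.2.3).

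Most rescued patients are non-responders anyway, because they met ETF, LCF or LPF or had PCR-confirmed recrudescence. The gap concerns rescue without any of these. At stake is the cure rate reported for each KAE609 dose: a patient who kept no KAE609 down and was cured by Coartem could appear as a KAE609 responder, against the protocol's rule.

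**Working it through.** The plan states no ACPR rate to reproduce. The check traces one patient through both documents and then sizes the effect.

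**Trace.** A KAE609 patient vomits the first dose and its replacement, receives Coartem on Day 1, meets no ETF, LCF or LPF criterion, and is smear-negative on Day 29.

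1. *Analysis set.* The full analysis set needs one dose taken and a positive baseline count (SAP 2.2). SAP 2.4.1 says vomiting does not remove a patient from the Safety set, which uses similar dose wording. Membership of the full analysis set is inferred from that.
2. *Follow-up.* Rescued patients stay in the study with all assessments (Protocol 5.5.6), so a Day 29 film is expected.
3. *Protocol 9.5.1.1.* Rescue for P. falciparum, not for a new infection: failure.
4. *SAP, Coartem classed as rescue* (as in Protocol 5.5.4). No rule in 2.7.2.1 applies, and the negative film gives a response.
5. *SAP, Coartem classed as non-rescue* (SAP 2.4.2, since no failure criterion was met). The drug is ignored, and the result is again a response.

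**Size per patient.** One responder in n patients is 1/n: 10 points at n = 10 and 5 points at n = 20.

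**Illustration.** The counts and days are assumed; they are not in the documents. Exact Clopper-Pearson 95% intervals:

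| Arm | Assumed outcomes | SAP as written | Protocol rule |
|---|---|---|---|
| n = 10 | 1 such rescue, 3 recrudescences | 7/10 = 70% (34.8 to 93.3) | 6/10 = 60% (26.2 to 87.8) |
| n = 20 | 1 such rescue, 6 recrudescences | 14/20 = 70% (45.7 to 88.1) | 13/20 = 65% (40.8 to 84.6) |

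**Kaplan-Meier at Day 29.** Rescue is on Day 1, with all others followed to recrudescence or Day 29. Recrudescences fall on Days 15, 22, 22 (n = 10) and Days 15, 15, 22, 22, 22, 29 (n = 20). Log-log intervals follow SAP 5.5.3.

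- Followed on as a responder: 7/10 = 70.0% (32.9 to 89.2); 14/20 = 70.0% (45.1 to 85.3).
- Event at rescue: 6/10 = 60.0% (25.3 to 82.7); 13/20 = 65.0% (40.3 to 81.5).
- Censored at rescue: 6/9 = 66.7% (28.2 to 87.8); 13/19 = 68.4% (42.8 to 84.4).

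If the Coartem is classed as rescue, both SAP curves follow the patient on. If it is classed as non-rescue, the curves part. The uncorrected curve censors any non-rescue antimalarial (2.7.2.1.2). The PCR-corrected curve censors only those given for other infections (2.7.2.1.1).

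**How often.** The documents give no rate. If each patient has chance q of such a rescue, the chance of at least one in an arm is 1 − (1 − q)^n:

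| Assumed q | n = 10 | n = 20 |
|---|---|---|
| 1% | 9.6% | 18.2% |
| 2% | 18.3% | 33.2% |
| 5% | 40.1% | 64.2% |

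The expected overstatement is q times the chance of a later negative smear, so at most q.

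**The case against.** **The protocol rule may still be in force.** SAP 2.1 ties the analysis to protocol section 9, Section 4 declares no change, and confining the as-if-not-taken rule to non-rescue drugs suggests that rescue was meant to be handled differently. This stands as far as intent goes. A reader might infer that the SAP deliberately reversed the protocol; the documents do not show that. The explicit derivation nevertheless gives the other answer, and nothing says which text prevails.

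**The affected group is narrow.** This largely stands. The investigator-judged 24-hour ETF criterion will capture some early rescues. Rescue after discontinuation for other reasons (Protocol 5.6.2) is a second route, but mainly in the 3-day arms, because in 1-day arms events after the assigned dose are not treatment discontinuation. The investigator-discretion wording in Protocol 5.5.6 might look like a third route, but it sits under a list of failure criteria and can be read as being about timing. Eligibility also excludes patients with severe vomiting or who cannot tolerate oral drugs.

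**The protocol does not settle the Kaplan-Meier handling.** This stands. A reader might infer that rescue must be an event. Yet the protocol censors antimalarials taken for reasons other than rescue for treatment failure, and rescue after a second vomit can be read as falling there. On that reading the gap is 70.0 − 66.7 = 3.3 points or 70.0 − 68.4 = 1.6 points, not 10 or 5.

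**Recrudescence and reinfection.** The absence of rescue censoring in SAP 2.7.2.4 and 2.7.2.5 might seem part of the same defect. For recrudescence, Protocol 9.5.1.4 has the same gap, and the SAP history logs the changed clearance condition. A new rule there would be a preference, not a correction.

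**Conclusion.** The omission is real and minor. As written, the SAP makes a patient in the full analysis set who is rescued without meeting ETF, LCF or LPF a responder if later smear-negative, whereas the protocol's rule for the proportion makes that patient a failure. The effect is 10 points per patient at n = 10 and 5 points at n = 20. For Kaplan-Meier, either reading of the protocol differs from a SAP that follows the patient on.

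This rests on two assumptions: that the programmer follows the SAP's own derivation, and that the full analysis set treats a vomited dose as taken. The number of such patients is unknown and may be zero. ACPR is secondary and descriptive, with no between-arm test. The per-protocol set largely excludes these patients, through the requirement that all KAE609 doses be taken and the exclusion for antimalarials without treatment failure. The primary hepatic endpoint and the liver-based escalation criteria are untouched.

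**What to change.** 1. In SAP 2.7.2.1, restore the protocol rule for ACPR proportions in the full analysis set: rescue for P. falciparum, other than for a new infection, is non-response. Exclude the end-of-study Coartem on Day 29, which SAP 2.4.2 classes as post therapy. Otherwise, declare and justify the change in SAP Section 4.
2. Align the definition of rescue in SAP 2.4.2 with the protocol's uses of the term, so that the same Coartem is classed the same way in every analysis.
3. State one Kaplan-Meier handling of rescue without a failure criterion, event or censoring at first use, and apply it to both curves.
4. Minor wording: in the Day X definitions of SAP 2.1.1.1, say ETF at any time, or LCF/LPF from Day 5. The general ACPR definition already settles Day 29, so this matters mainly for Day 15.

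The cost is a few sentences and reprogramming of derived variables. Rescue use and blood films are already collected. Reporting the number of affected patients per arm would show whether any result moves; if there are none, items 1 to 3 change no figure.
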